7. SELECTION AND WITHDRAWAL OF SUBJECTS

7.1. Subject Inclusion Criteria

Only subjects meeting the following criteria are eligible for study participation.

- 1. Subjects must be males or females age 18 years or older.
- 2. Subjects with Stage 1-4 (per the Modified Keystone Grading Schema) acute GVHD of the lower GI tract, without signs of chronic GVHD, at the time of diagnosis, which developed in the first 180 days following allogeneic hematopoietic cell transplantation (HCT) using bone marrow, peripheral blood or cord blood; or after pre-planned donor lymphocyte infusion.
- 3. Subjects are willing to undergo or must have had an endoscopy of the upper and/or lower GI tract and biopsy to confirm GI GVHD within 7 days of screening. Biopsy results are not needed to initiate treatment; however, if GI GVHD is not confirmed histologically, treatment with ALXN1007 will be discontinued.
- 4. Subjects must be receiving systemic corticosteroids.
- 5. Subjects with an absolute neutrophil count (ANC) >500/µL at Screening.
- 6. Subjects and spouse/partner who are of childbearing potential must be using highly effective contraception consisting of 2 forms of birth control (at least 1 of which must be a barrier method) starting at Screening and continuing through the entire study (for at least 3 months after the last dose of ALXN1007 if study treatment is stopped early or subject withdraws consent). Highly effective contraception is defined as:
 - a. Established use of oral, injected or implanted hormonal methods of contraception.
 - b. Placement of an intrauterine device or intrauterine system.
 - c. Double barrier methods of contraception: condom or occlusive cap (diaphragm or cervical/vault caps) with spermicidal foam/gel/film/cream/suppository (double barrier method will count as 2 forms of contraception).
- 7. Male subjects must not donate sperm during the Screening and Treatment Periods, and for at least 3 months after the last dose of ALXN1007.
- 8. Subjects are willing and able to give written informed consent and to comply with all study visits and procedures.

7.2. Subject Exclusion Criteria

Subjects meeting any of the following exclusion criteria should not participate in this study.

- 1. Subjects with a body weight > 140 kg (for Cohorts dosing 20 mg/kg of ALXN1007 and higher only).
- 2. Subjects with signs and symptoms of chronic GVHD.
- 3. Subjects with an active uncontrolled infection. An active uncontrolled infection is defined as hemodynamic instability attributable to sepsis or new symptoms, worsening

- physical signs or radiographic findings attributable to infection. Persisting fever without signs or symptoms will not be interpreted as an active uncontrolled infection. (Subjects with a controlled infection receiving definitive therapy for 72 hours prior to enrollment [ie, Screening Visit/sign ICF] are eligible.)
- 4. Subjects who test positive for *C. difficile* from a sample collected up to 3 days prior to Screening/sign ICF.
- 5. Subjects known to be infected with human immunodeficiency virus (HIV), hepatitis B or hepatitis C.
- 6. Subjects with relapsed/persistent malignancy requiring rapid immune suppression withdrawal.
- 7. Subjects who received an unplanned (not part of the original transplant therapy plan) donor lymphocyte infusion.
- 8. Subjects who received previous systemic treatment for acute GVHD, except for a maximum of 3 days (72 hours) of 2 mg/kg methylprednisolone (or equivalent dose of prednisone).
- 9. Subjects who received any corticosteroid therapy (for indication other than GVHD) at doses >0.5 mg/kg/day methylprednisolone equivalence within 7 days prior to the onset of GVHD therapy.
- 10. Subjects with unresolved veno-occlusive disease of the liver defined as persistent bilirubin abnormalities not attributable to GVHD and ongoing organ dysfunction (renal, ascites).
- 11. Subjects known to have an uncontrolled thyroid disorder.
- 12. Subjects who are pregnant, breast feeding or sexually active and unwilling to use effective birth control for the duration of the study.
- 13. Subjects with creatinine clearance (CrCl) <40 mL/minute, as calculated by the Cockcroft-Gault formula (Cockcroft-Gault CrCl = [140-age] × [Wt in kg] × [0.85 if female] / [72 × Cr]).
- 14. Subjects participating in any investigational drug trial, or with exposure to any other investigational agent, device and/or procedure, beginning at Screening and throughout the entire trial. Investigational drugs, devices and/or procedures must be discontinued upon enrolling (ie, Screening/sign ICF) into this study.
- 15. Subjects with any medical or psychological condition that, in the opinion of the Investigator, might interfere with the subject's participation in the trial, pose any additional risk for the subject, or confounds the assessments of the subject.
- 16. Subjects with prior exposure to ALXN1007 or known allergies, hypersensitivity or intolerance to ALXN1007 or its excipients.

7.3. Subject Withdrawal Criteria

The Investigator should notify the Sponsor and their site monitor of all study withdrawals as soon as possible.

Subjects may withdraw consent at any time. Every effort should be made to ensure subjects are willing to comply with study participation prior to conducting the screening procedures and the subject should be fully informed of the restrictions related to the change of concomitant medications during the study.

Investigators may choose to discontinue a subject's treatment because of an AE as well as conditions or illnesses that preclude compliance with the protocol from the standpoint of the subject's safety or well-being (safety, behavioral or administrative reasons).

Subjects should be permanently discontinued from ALXN1007 treatment if any of the following occur during the study:

- Serious infusion reaction (such as bronchospasm with wheezing or requiring ventilatory support or symptomatic hypotension, refer to Section 9.5.1) or serum sickness-like reactions manifesting 1 to 14 days after drug administration;
- A Grade 4 AE related to study treatment;
- Severe uncontrolled infection;
- Malignancy other than non-melanoma skin cancer or relapse of the disease for which the bone marrow transplant was performed;
- Meningococcal infection;
- Initiation of protocol prohibited medications;
- Pregnancy or planned pregnancy; or
- If the Alexion Medical Monitor and/or the Investigator deem it is in the best interest of the subject (eg, the subject is unable to tolerate the minimum ALXN1007 dose for the study; see Section 6.4.1).

Subjects who withdraw, or are withdrawn, from the study will not be replaced with a newly enrolled subject, with the exception of subjects who do not have biopsy confirmation of GI GVHD (see Sections 6.1.5 and 7.3.2).

7.3.1. Pregnancy and Breast Feeding

Reproduction and development studies with ALXN1007 have not been performed. ALXN1007 should not be administered to women who are pregnant or breast feeding (please refer to Section 11.2.8 for additional information).

7.3.2. Handling of Withdrawals and Discontinuation from Study Treatment

The following procedures will be followed when a subject withdraws or is withdrawn from study participation:

- If the subject withdraws consent prior to the Day 180 visit, the ET visit should be performed for safety at the time of consent withdrawal (within 5 days), if subject allows.
- Subjects must continue antibiotic prophylaxis active against meningococcal infection for 6 weeks after the last dose of ALXN1007.

• The reason(s) for withdrawal will be recorded in the subject's source documents and the eCRF.

The following procedures will be followed when an investigator discontinues a subject from study treatment:

- In the event of early discontinuation from study treatment, subjects will be requested to return for the remainder of the scheduled study visits through the Day 180 visit.
- In the event that the biopsy results do not confirm GI GVHD, study treatment will be discontinued and an ET visit will be performed 6 weeks (+/- 5 days) after the last dose of ALXN1007 was received.
- If a subject discontinues study treatment due to an AE, the event will be followed until it is resolved or, in the opinion of the PI, the subject is determined to be medically stable. Subjects will be requested to return for the remainder of the scheduled study visits through the Day 180 visit.

For female subjects who become pregnant, please refer to Section 7.3.1.

Subjects who fail to return for final assessments will be contacted by the site study staff members in an attempt to have the subjects comply with the protocol. As it is vital to obtain follow-up data, every effort must be made to undertake protocol-specified follow-up procedures. Follow-up due diligence documentation will consist of 3 phone calls followed by 1 registered letter to the subject's last known address. Refer to the SOM for additional information.

8. TREATMENT OF SUBJECTS

8.1. Description of Study Drug

ALXN1007 is a humanized, anti C5a monoclonal antibody formulated to 10 mg/mL. ALXN1007 will be diluted with 0.9% sodium chloride for injection, United States Pharmacopeia (USP).

Further details on study drug description and preparation and administration instructions are provided in the current version of the ALXN1007 IB and the Pharmacy Manual.

8.2. Prior and Concomitant Medications and Therapies

Prior and concomitant medications and therapies will be recorded on the eCRF as follows:

- All medications and therapies from 7 days prior to signing the ICF through 30 days after the last dose of ALXN1007.
- All medications and therapies used to treat SAEs occurring through the Day 180 visit.

8.2.1. Hematopoietic Cell Transplantation Information (Including Conditioning Regimen)

Details on HCT performed will also be recorded on the eCRF as follows:

- All medications or treatments including, but not limited to, anti-thymocyte globulin (ATG), alemtuzumab, irradiation, and chemotherapy, received as part of the conditioning regimen in preparation for HCT.
- Additional information related to HCT including, but not limited to, transplant date, donor sex, donor cytomegalovirus (CMV) serostatus, donor type (eg, matched related, matched unrelated, mismatched), graft source (eg, bone marrow, peripheral blood, cord blood), manipulation of graft source (eg, T cell depletion), and post-transplant GVHD prophylaxis regimen.

8.2.2. Immunosuppressive Medications

GVHD prophylaxis should be based on institutional practice. Subjects developing acute GVHD during GVHD prophylaxis (ie, while on calcineurin inhibitors, sirolimus, etc) should have their prophylaxis medication continued during the study period unless discontinuation is clinically indicated (eg, for management of toxicity). Medications such as cyclosporine (CSA), tacrolimus or sirolimus (if used as GVHD prophylaxis when acute GVHD developed) should be continued at therapeutic doses and adjusted as necessary for renal, central nervous system or other toxicity using conventional management guidelines. The recommended therapeutic trough level of CSA is 200-400 ng/mL measured by whole blood high-performance liquid chromatography (HPLC), and institutional levels for other assays. The recommended therapeutic trough level is 5-15 ng/mL for tacrolimus and 3-12 ng/mL for sirolimus.

Subjects may be switched to an alternate immunosuppressive regimen as clinically indicated or based on side effects at the discretion of the Investigator. Dose adjustments for CSA should be

made based on serum bilirubin and creatinine. As applicable, drug levels of CSA, tacrolimus and sirolimus should be obtained at Baseline and on dosing on Days 7, 21, 35 and 49, as well as the ET visit. The timing of sample collection (eg, trough) should be appropriate for the drug being monitored and not coupled with the timing of administration of ALXN1007. This will be done for monitoring and dose adjustment per standard of care, or more frequently as needed. These immunosuppressants may result in a variety of drug interactions, which may require dose adjustments:

- Cyclosporine (CSA): Dosing should follow institutional practice with typical regimens consisting of initial IV CSA dose followed by tapering and then oral dosing with tapering.
- **Tacrolimus:** Dosing should follow institutional practice with typical regimens consisting of initial IV tacrolimus dose followed by tapering and then oral dosing with tapering.
- **Sirolimus:** Dosing should follow institutional practice with typical regimens consisting of an oral loading dose followed by tapering.
- **Mycophenolate mofetil:** Dosing should follow institutional practice with typical regimens consisting of oral dosing.
- Intravenous immunoglobulin (IVIG): Dosing should follow institutional practice.

8.2.3. Corticosteroids

All subjects treated in this trial will receive corticosteroids at a suggested dose equivalent to prednisone 2 mg/kg/day PO (orally) (or methylprednisolone 1.6 mg/kg/day IV) as therapy for acute GVHD with maximal doses determined per institutional guidelines and adjusted per ideal body weight (IBW) as suggested below. Corticosteroids may be given in divided doses. Subjects unable to tolerate oral prednisone (or equivalent) due to nausea, or for whom absorption is a concern, should be prescribed IV methylprednisolone. Corticosteroid tapering may follow local institutional practice. The corticosteroid dose should not be tapered to less than 0.25 mg/kg/day prednisone (or equivalent) (or 0.2 mg/kg/day methylprednisolone) prior to 28 days following corticosteroid initiation.

Suggested IBW Dosing Guidelines

- If subject weighs less than 100% of IBW, dosing is based on actual body weight.
- If subject weighs 100% to 120% of IBW, dosing is based on IBW.
- If subject weighs more than 120% of IBW, dosing is based on adjusted body weight per institutional guidelines.
- Maximum weight for dosing is 100 kg.

Corticosteroid dose should be rounded based on pill strength (for example, 5 or 10 mg for prednisone; 4 or 8 mg for methylprednisolone).

The following is a *suggested* prednisone taper for responders. Variations from the regimen suggested below are allowed based on the discretion of the Investigator.

Suggested Prednisone Taper for Responders:

- Days 1-5: 2 mg/kg/day of prednisone PO (or 1.6 mg/kg/day of methylprednisolone IV) divided once or twice/day.
- Days 6-10: 1.5 mg/kg/day of prednisone once daily.
- Days 11-15: 1 mg/kg/day of prednisone once daily.
- Days 16-20: 0.5 mg/kg/day of prednisone once daily.
- Days 21-28: 0.25 mg/kg/day of prednisone once daily.

Subjects should be tapered as tolerated to no less than 0.25 mg/kg/day (methylprednisolone 0.2 mg/kg/day) prior to 28 days following corticosteroid initiation; then tapered according to institutional guidelines with a goal to reach <0.2 mg/per/kg per day PO of prednisone or <0.16 mg/per/kg IV per day of methylprednisolone by Day 56.

8.2.4. Prevention of Infection and Prophylactic Antibiotics

Prophylactic antimicrobials to prevent bacterial, fungal and viral infections will be administered based on each institution's practice but must include agents directed against Herpes simplex virus, *Pneumocystis jiroveci*, and bacterial and fungal infections. A pre-emptive monitoring and treatment strategy for CMV is required.

Subjects must continue or begin antibiotic prophylaxis active against meningococcal infection prior to receiving the first dose of ALXN1007. Subjects already receiving empirical antibiotic prophylaxis for bacterial infections or therapeutic antibiotic treatment must be receiving an antibiotic throughout the treatment period and for 6 weeks after the last dose of ALXN1007 that is active against encapsulated organisms (including *N. meningitidis*) based on institutional guidelines. If subjects are receiving prophylactic, empirical or therapeutic antibiotic treatment with drugs that have activity against meningococcus (and pneumococcus), no additional antibiotic prophylaxis will be required during that treatment period.

8.2.5. Supportive Care

Subjects will receive treatment based on each center's standard of care practice with respect to supportive care. Nutritional practices with respect to diet and total parenteral nutrition will be instituted by each center's standard practice and recorded on the eCRF. Blood transfusion support and growth factors may be provided based on institutional practices and should be clearly recorded in the eCRF.

8.2.6. Cytotoxic, Biologic and Investigational Agents

Upon enrolling into this study, ie, Screening Visit/sign ICF, any investigational drugs, devices and/or procedures the subject may be receiving (or using) must be discontinued. Cytotoxic, biologic or investigational agents are not permitted throughout the study. These include, but are not limited to, ATG, Alemtuzumab, Rituximab, photopheresis, and Thalidomide.

8.3. Treatment Compliance

All instances of noncompliance and all significant protocol violations will be reported to the appropriate ethics committee per local regulations and reported to the Sponsor or representative.

The infusion of ALXN1007 into subjects will be under the supervision of the PI or designee to ensure that the subject receives the appropriate dose at the appropriate time points during the study and that adequate safety monitoring (both during and up to 2 hours after the infusion) occurs (see Section 9.5.1).

Subjects who fail to return for a scheduled visit within the accepted intervals must be contacted by the site study staff to determine the reason for missing the appointment. Instructions for handling of missing visits are provided in Section 6.1.6.

8.4. Randomization and Blinding

This is an open-label non-randomized study.

Dosing cohort assignment must be documented in the subject's source documents at the investigational site and in the eCRF for the study. The Sponsor or designee will also maintain documentation of dosing cohort assignment for subjects enrolled in the study.

9. STUDY DRUG MATERIALS AND MANAGEMENT

9.1. Study Drug

ALXN1007 is a humanized, anti-C5a monoclonal antibody formulated at 10 mg/mL. The sterile formulation is supplied by the Sponsor in a single use 20 mL vial. Each vial contains a total extractable dose of 150 mg per vial. Refer to Table 8 and the current IB for additional information.

Table 8: Study Drug

	Study Drug
Product Name	ALXN1007
Dosage Form	Concentrated solution for infusion
Unit Dose	150 mg
Nominal Fill Volume	15 mL
Route of Administration	Intravenous (IV) infusion
Physical Description	Clear, colorless solution practically free from particles in a 20 mL vial
Manufacturer	Alexion Pharmaceuticals, Inc.

9.2. Study Drug Packaging and Labeling

ALXN1007 is packaged in Type 1 borosilicate glass vials and stoppered with a butyl rubber stopper with an aluminum overseal and a flip-off cap. The study drug will be supplied in a one vial per kit configuration.

Each kit will have a label describing the contents and a place for the pharmacist to record the subject study number and initials. Please refer to the ALXN1007 Pharmacy Manual to see an example kit label.

ALXN1007 will be released to each site upon receipt of all required essential documents based upon federal, state and local regulations.

9.3. Study Drug Storage

Upon arrival at the study site, the pharmacist should promptly remove ALXN1007 from the shipping cooler and store in refrigerated conditions at 2°C to 8°C (35 to 47°F) and protected from light. ALXN1007 must be stored in a secure, limited-access storage area and the temperature must be monitored daily.

The ALXN1007 drug product should be allowed to warm to room temperature prior to administration. The material must not be heated (for example, by using a microwave or other heat source) other than by ambient air temperature.

Please consult the ALXN1007 Pharmacy Manual for further information regarding the storage conditions and administration of reconstituted ALXN1007.

9.4. Study Drug Preparation

ALXN1007 is dosed on a mg/kg basis. The subject's dose of ALXN1007 will be further diluted into 0.9% sodium chloride solution for injection USP at the volume specified in the ALXN1007 Pharmacy Manual. Doses of ALXN1007 must only be prepared and dispensed by a Pharmacist or a medically qualified staff member. ALXN1007 is to be dispensed only to subjects enrolled (ie, signed ICF) and who are confirmed eligible for participation in this study. Once ALXN1007 is prepared for a subject, it can only be administered to that subject. ALXN1007 vials are for one time use only and any drug product remaining in the vial should not be used for another subject. Any drug remaining in the infusion tubing or sodium chloride 0.9% bag should not be used for another subject.

9.5. Administration

ALXN1007 should NOT be administered as an IV Push.

ALXN1007 solution in sodium chloride 0.9% will be administered to the subject using an IV tubing administration set via an infusion pump. Use of an in-line filter for infusion is recommended. For subjects receiving a 10 mg/kg ALXN1007 dose, IV infusions must be administered over 1 hour \pm 10 minutes. For subjects receiving a 20 mg/kg ALXN1007 dose, IV infusions must be administered over 2 hours \pm 10 minutes.

For subjects on a weekly dosing schedule, there should be a minimum of 4 days between ALXN1007 doses. For subjects on a twice weekly dosing schedule, there should be a minimum of 2 days between ALXN1007 doses. If the recommended acceptable windows cannot be observed, the Sponsor or its representative must be contacted prior to scheduling a visit.

Further details on ALXN1007 preparation and administration for doses being investigated in this study can be found in the Pharmacy Manual.

9.5.1. Management of Potential Drug Infusion Reactions

Infusion of other monoclonal antibodies has been associated with infusion reactions, with onset typically during or shortly after completion of the infusion. For this reason, subjects will be carefully observed during each infusion. Subjects will remain under observation for 2 hours after the infusion.

Subjects who develop AEs of rash, hives, itching and/or dysphagia of mild to moderate severity during their infusion of ALXN1007 may continue to be infused if deemed to be medically appropriate by the Investigator. Medical intervention may include, but is not limited to, slowing of the infusion rate (with or without treatment) or stopping the infusion, with a total infusion time not to exceed 3 hours. Any acute reaction should be treated according to standard medical practice depending upon clinical signs and symptoms. The AE and any associated concomitant medications must be captured in the subject's source document and eCRF.

Some subjects treated with IV infusions of monoclonal antibodies have experienced concurrent infusion-related reactions with signs or symptoms that can be classified as acute allergic reactions/hypersensitivity reactions or cytokine release syndrome. The signs and symptoms include headache, fever, facial flushing, pruritus, myalgia, nausea, chest tightness, dyspnea, vomiting, erythema, abdominal discomfort, diaphoresis, shivers, hypertension, lightheadedness,

hypotension, palpitations and somnolence. Anaphylaxis might occur at any time during an infusion and subjects will be monitored closely prior to and through 2 hours following the end of the infusion. In addition, the re-administration of some monoclonal antibodies has been associated with serum sickness-like reactions manifesting 1 to 14 days after drug administration. All AEs which may indicate an infusion related response will be graded according to criteria from the Common Terminology Criteria for Adverse Events (CTCAE) version 4.03.

Before any infusion is started, the treating physician and other appropriate personnel must make certain medication (adrenaline, inhaled beta agonists, antihistamines and corticosteroids) and other requirements to treat anaphylaxis are readily available. The infusion must be stopped immediately if \geq Grade 2 allergic/hypersensitivity reactions (including drug fever) or \geq Grade 3 cytokine release syndrome/acute infusion reaction occurs. The Sponsor must be notified within 24 hours of any infusion reaction requiring interruption of study drug.

Subjects experiencing a reaction during the administration of study drug should be treated according to institutional guidelines. For a Grade 1 or Grade 2 infusion-related reaction, the infusion should be stopped and medication with antihistamine (eg, with diphenhydramine 25 mg to 50 mg PO or equivalent), and acetaminophen (650 mg PO or equivalent) may be considered. If the signs and symptoms have resolved with the above medication(s), the infusion may be restarted. However, the subjects should be infused at a slower rate and be monitored closely for any signs and symptoms of infusion-related reactions during the remainder of the infusion. The study drug should be stopped if the infusion reaction recurs and subsequent doses may not be given. Subjects experiencing an infusion reaction should be observed in the clinic until resolution of the reaction, or until the PI determines the subject is no longer at risk.

If an event of anaphylaxis occurs, according to the criteria in Table 9, then subcutaneous epinephrine (1/1000, 0.3 to 0.5 mL or equivalent) should be considered. In the case of bronchospasm, inhaled beta agonist also should be considered. Subjects administered antihistamine for the treatment or prevention of infusion reactions should be given appropriate warnings about drowsiness and impairment of driving ability prior to discharge.

In the event of anaphylaxis no further doses of ALXN1007 will be given.

Table 9: Clinical Criteria for Diagnosing Anaphylaxis

Anaphylaxis is highly likely when any 1 of the following 3 criteria is fulfilled:

- 1. Acute onset of an illness (minutes to several hours) with involvement of the skin, mucosal tissue, or both (eg, generalized hives, pruritus or flushing, swollen lips-tongue-uvula), AND at least one of the following:
 - a. Respiratory compromise (eg, dyspnea, wheeze-bronchospasm, stridor, reduced PEF, hypoxemia)
 - b. Reduced BP or associated symptoms of end-organ dysfunction (eg, hypotonia [collapse], syncope, incontinence)
- 2. Two or more of the following that occur rapidly after exposure to a likely allergen for that subject (minutes to several hours):
 - a. Involvement of the skin-mucosal tissue (eg, generalized hives, itch-flush, swollen lips-tongue-uvula)
 - b. Respiratory compromise (eg, dyspnea, wheeze-bronchospasm, stridor, reduced PEF, hypoxemia)
 - c. Reduced BP or associated symptoms (eg, hypotonia [collapse], syncope, incontinence)
 - d. Persistent GI symptoms (eg, crampy abdominal pain, vomiting)
- 3. Reduced BP after exposure to known allergen for that subject (minutes to several hours):
 - a. Systolic BP of less than 90 mm Hg or greater than 30% decrease from that person's baseline

Abbreviations: BP = blood pressure; PEF = peak expiratory flow (Sampson, 2006)

Subjects who experience a severe reaction during administration of study drug resulting in discontinuation of study drug will have blood drawn for determination of drug concentration, antibodies to ALXN1007 and complement proteins (ie, C5, C5a, C5b9). Samples should be obtained within 3 hours of the onset of the reaction and 1 week following disappearance of all symptoms. Such subjects should undergo all scheduled safety evaluations required by the protocol.

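### Section 9.5.1 lets an infusion continue through moderate hives or itching, orders an immediate stop for Grade 2 allergic reactions, and does not say which instruction prevails

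*Protocol*

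**What the plan says.** Most of the relevant text is in Protocol Section 9.5.1.

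- **Permission (second paragraph).** Subjects with rash, hives, itching or dysphagia of "mild to moderate severity during their infusion of ALXN1007 may continue to be infused if deemed to be medically appropriate by the Investigator". The interventions named include "slowing of the infusion rate (with or without treatment) or stopping the infusion", with total infusion time capped at 3 hours.
- **Signs and grading (third paragraph).** Infusion-related signs, pruritus and erythema among them, "can be classified as acute allergic reactions/hypersensitivity reactions or cytokine release syndrome". Events that may indicate an infusion response are graded by CTCAE v4.03.
- **Mandatory stop (fourth paragraph).** "The infusion must be stopped immediately if" either of two thresholds is met. One is "Grade 2 allergic/hypersensitivity reactions (including drug fever"), at that grade or above. The other is cytokine release syndrome or acute infusion reaction at Grade 3 or above.
- **Recommended stop (fifth paragraph).** "For a Grade 1 or Grade 2 infusion-related reaction, the infusion should be stopped". Medication may be considered, and the infusion may restart at a slower rate once signs and symptoms have resolved.

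Two other sections bear on this. Section 6.4.2 leaves slowing or stopping to the Principal Investigator for any adverse reaction during administration, and points to 9.5.1 for advice. Section 11.2.3 gives a severity scale for terms that CTCAE does not describe, in which Grade 1 is mild and Grade 2 is moderate.

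**The concern.** The permission and the mandatory stop can apply to the same event. Moderate hives during an infusion, judged allergic, fall under the permission by symptom and severity word, and under the mandatory stop by type and grade. An Investigator who relies on the permission and only slows the infusion would be following one sentence of the protocol and breaching another. The breached sentence is the stronger one, and it protects subjects against a reaction type that can progress. What is at stake is subject safety at the bedside and a clear standard for judging compliance. No estimate or test depends on it.

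**Working it through.** There is no figure to reproduce. The check is to set the instructions side by side and see where they meet.

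**Step 1: does the permission allow continuing without a stop?** Yes. The second paragraph of 9.5.1 joins slowing and stopping with *or*, so slowing alone is a permitted response. Reading *continue* as restarting after a stop does not remove that option.

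**Step 2: can the named symptoms be allergic reactions?** Itching can: pruritus is in the third paragraph's list of signs. Hives are not in that list, but Table 9 names generalized hives, with pruritus, as skin signs in its anaphylaxis criteria. Table 9 criteria 1 and 2 need a further feature as well, so isolated hives do not meet the definition of anaphylaxis. The table shows only that the protocol treats hives as an allergic sign. Dysphagia has no such link in the text. A rash judged to be GVHD is not a reaction and falls outside the conflict.

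**Step 3: is moderate the same as Grade 2?** The permission uses severity words and the stop uses grades. The only mapping in the documents is the Section 11.2.3 scale, which applies when CTCAE does not describe the term. CTCAE v4.03 itself is not reproduced, so its grading of moderate hives cannot be checked here. The mapping is therefore an assumption.

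**Step 4: compare the rules under that assumption.**

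| Reaction during infusion | Second paragraph | Fourth and fifth paragraphs | Result |
|---|---|---|---|
| Grade 2, allergic/hypersensitivity | may continue | must stop | hard conflict |
| Grade 1, allergic/hypersensitivity | may continue | should stop | softer conflict |
| Grade 2, other infusion-related | may continue | should stop | softer conflict |
| Grade 1, other infusion-related | may continue | should stop | softer conflict |

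The Grade 3 stop for cytokine release syndrome or acute infusion reaction lies above mild to moderate and does not meet the permission.

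**Step 5: does any other text settle precedence?** No. Section 6.4.2 repeats the discretion without making it subject to the mandatory stop. Section 7.3 concerns permanent discontinuation and, among infusion reactions, lists serious ones and serum sickness-like reactions. The fifth paragraph of 9.5.1 defers treatment of reactions to institutional guidelines, but does not allow those guidelines to override the protocol's own stop.

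**The case against.** The strongest reply is that a conditional permission gives way to a specific obligation. An Investigator who stops complies with both paragraphs, and the permission itself lists stopping as an option. That much stands: a reader might infer that the two instructions cannot both be obeyed, and the documents do not support that. What remains is that the permission, used as written, leads to a breach, and no phrase says that it yields.

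A second reply is that the permission never mentions Grade 2 or an allergic reaction. This also stands in part. The conflict needs the Section 11.2.3 mapping and the Investigator's judgement that the event is allergic. But if moderate does not mean Grade 2, the permission has no ceiling on the scale used to grade these events, and the same edit is needed.

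Third, a reader might infer that slowing instead of stopping avoids the rapid report to the sponsor. The text does not support this: "The Sponsor must be notified within 24 hours of any infusion reaction requiring interruption of study drug". A Grade 2 allergic reaction requires interruption under the mandatory stop, whatever the Investigator does. Recording of the event is also required on either route.

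Fourth, a reader might want to size the problem by the number of planned infusions. That total would not be a bound, because subjects without biopsy confirmation can be dosed and replaced, and the cohort sizes for Cohorts 2 and 3 are approximate. It would also say nothing about how many infusions are affected.

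Other safeguards remain in force, including 2 hours of observation, rescue medication at hand, and no further dosing after anaphylaxis. They limit the harm but do not resolve the wording.

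**Conclusion.** The point holds as a wording conflict in a safety instruction. Of the four combinations of grade and type in the table, one sets a permission against a mandatory stop (Grade 2 allergic or hypersensitivity reactions), and three set it against a recommended stop. The hard case rests on two conditions: that moderate is read as Grade 2, and that the Investigator classifies the event as allergic. The number of infusions affected is unknown, because the documents give no reaction rate. No endpoint, analysis, error rate or sample size changes. The text should be corrected because a subject could be kept on an infusion that the same section says must stop.

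**What to change.** In the second paragraph of Section 9.5.1, replace the severity words with CTCAE v4.03 grades and add: *subject to the stopping rules below in this section; any Grade 2 or higher allergic/hypersensitivity reaction requires immediate stop*. In Section 6.4.2, add *subject to Section 9.5.1* to the sentence that gives the Principal Investigator discretion.

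The second and fifth paragraphs of 9.5.1 should also agree on Grade 1 reactions. Whether a Grade 1 reaction calls for a stop and restart or for slowing alone is a clinical choice for the sponsor's clinicians.

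The cost is a few words in two sections, with no effect on visits, data collection or analysis. SAP Section 4.1 records that the study ended early, so the main benefit now is that the conflicting text is not carried into another protocol.
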